7.3 Preparation/Handling/Storage/Accountability

Acquisition and Accountability

The investigational TELLTALE systems will be shipped to sites and stored in a secured location with a written receipt and accountability log. Alternatively the systems may be transported and handled by manufacturer representatives, and comparably recorded in the accountability log.

Formulation, Appearance, Packaging, and Labeling

This is described in the manufacturer instructions for use.

Product Storage and Stability

This is described in the manufacturer instructions for use.

Preparation

The TELLTALE system is prepared according to the accompanying manufacturer instructions for use.

7.4 Measures to Minimize Bias: Randomization and Blinding

Not applicable for an open-label study.

7.5 Study Intervention Compliance

Protocol compliance will be assured by source document (medical record) to case-report-form data verification by independent data monitors.

7.6 Concomitant Therapy

There are no restrictions on concomitant therapy.

8 DISCONTINUING OR WITHDRAWING STUDY INTERVENTION OR SUBJECT

8.1 Discontinuation of Study Intervention

The TELLTALE guidewire system is a single-use device with no components implanted. It is used during a single BASILICA-TAVR procedure involving a permanent implant that is not intended to be removed.

8.2 Aborted or abandoned TELLTALE BASILICA-TAVR

In the case of aborted TELLTALE BASILICA-TAVR without successful leaflet laceration, subjects may go off-study as soon as they are clinically stable, but at least 30 day follow-up. Such subjects need not undergo additional follow-up for exploratory efficacy or natural history assessment.

8.3 Subject Discontinuation/Withdrawal from the Study

Reasonable efforts will be made to undertake protocol-specified safety follow-up procedures to capture adverse events and adverse device effects, both serious and not, as well as unanticipated problems, through the 30-day follow-up visit.

Subjects are free to withdraw from participation in the study at any time upon request. If a subject repeatedly and consistently declines to return for follow-up evaluation, the investigators may be forced to withdraw the subject from the study prematurely.

However, since the study intervention (TELLTALE BASILICA-TAVR procedure) will already have been performed, withdrawal means these subjects would be withdrawing from follow-up of endpoints and adverse events. For the sake of safety, subjects will be advised not to withdraw.

Pregnancy after TELLTALE BASILICA-TAVR will not lead to study discontinuation because there is no research-related radiation or other research procedures that threaten the fetus or the pregnancy.

8.4 Loss to Follow-up

A subject will be considered lost to follow-up if he or she fails to return for 2 consecutive scheduled visits and despite attempts at contact by the study site staff.

The following actions must be taken if a subject fails to return to the enrollment center for a required study visit:

- The site will attempt to contact the subject and reschedule the missed visit and counsel the subject on the importance of maintaining the assigned visit schedule and ascertain if the subject wishes to and/or should continue in the study.
- Before a subject is deemed lost to follow-up, the investigator or designee will make every effort to regain contact with the subject (where possible, 3 telephone calls to the subject, contact to the referring physician, and, if necessary, a certified letter to the subject's last known mailing address or local equivalent methods). These contact attempts should be documented in the study file.
- Should the subject continue to be unreachable, he or she will be considered to have withdrawn from the study with a primary reason of "lost to follow-up."

9 STUDY ASSESSMENTS AND PROCEDURES

9.1 Screening Procedures

Screening prior to consent is based entirely on clinically-indicated medical encounters, blood tests, laboratory and clinical examinations (cardiac catheterization, echocardiography, CT, MRI, blood tests), review of medical records, and communication with candidates (in-person, via telephone, via telepresence, in writing, or via email).

The screening data are reviewed by the local multidisciplinary heart team, and then are reviewed by the Central Clinical Eligibility Committee before screening is complete. Candidates are only invited to participate if eligible.

Some sites will use a screening consent to abide local institutional requirements before transmitting medical records to screen for eligibility.

Screening centers will comply with Health Insurance Portability and Accountability Act (HIPAA) if applicable.

9.2 Efficacy Assessments

Efficacy assessments are performed by qualified laboratories and staff at enrolling centers. Standard clinical examinations (such as vital signs and symptom classification), clinical blood testing, and clinical cardiac imaging procedures (such as echocardiography, cardiac CT, cardiac MRI) are performed by clinical laboratories at the enrolling centers.

CT assessments (on baseline exam, not efficacy): valve-to-coronary (VTC) and valve-to-sinus (VTS) distance. These are analyzed by a NHLBI core laboratory.

Fluoroscopy assessments (post-TAVR coronary arteriography) includes coronary patency and ability to engage the coronary artery ostium with a catheter. These are analyzed by a NHLBI core laboratory.

Echocardiography assessments include transvalvular gradient, paravalvular leak, mitral valve injury. These echocardiographic assessments are standard and do not require core lab analysis. These are not analyzed by a NHLBI core laboratory. Instead, parameters are extracted for official reports from local echocardiography laboratories. As a result, certain fields may be missing for individual or focused examinations, such as volumes, continuity-equation valve areas, etc. These will be recorded as missing and not as protocol deviations.

Standard research assessments (questionnaires such as KCCQ-23) are performed by qualified staff at enrollment centers according to a study Manual of Operations and according to an instruction-oriented Case Report Form.

9.3 Safety and Other Assessments

Standard safety assessments (adverse event assessments) are performed by qualified staff at enrollment centers according to the Protocol Schedule of Activities and a study Manual of Operations and according to an instruction-oriented Case Report Form.

Safety assessments follow a structured adverse event case report form and are corroborated by independent data monitors and, for primary endpoints, by an independent clinical events adjudication committee.

Assessment of neurovascular events (stroke and TIA)

For candidates without prior stroke or transient ischemic attack (TIA), formally-trained and certified research coordinators will perform baseline assessments of modified Rankin Score and

NIH Stroke Score. If there is no clinically evident TIA or stroke, the predischarge assessments of modified Rankin Score and NIH Stroke Score will be performed by certified research coordinators. Otherwise they will be performed by consulting neurology specialists.

For candidates with prior stroke or TIA, consulting neurology specialists will perform baseline and pre-discharge assessments including modified Rankin Score and NIH Stroke Score.

Training and certification will be obtained from a service such as BlueCloud.

9.4 Adverse Events and Serious Adverse Events

In this protocol, TAVR is clinically indicated. BASILICA using the TELLTALE Guidewire System is performed for the purpose of research.

Definition of Adverse Event

Adverse events: Any untoward medical occurrence in a human subject, including any abnormal sign (e.g., abnormal physical exam or laboratory finding), symptom, or disease, temporally associated with the subject's participation in the research, whether or not considered related to the subject's participation in the research (21 CFR 312.32 (a)).

This includes:

- Expected events related to the subject's disease process during active enrollment in the research protocol and do not directly result from use of the investigational device or study.
- Procedural events directly related to the BASILICA-TAVR cardiac catheterization procedure and recovery from the procedure and do not directly result from use of the investigational device.

Definition of Serious Adverse Events (SAE)

Serious Adverse Event (SAE): A serious adverse event that results in any of the following and NOT directly related to the device (21 CFR 812.3(s)). This includes any event that

- Results in death
- Is life-threatening (places the subject at immediate risk of death from the event as it occurs);
- results in in-patient hospitalization or prolongation of existing hospitalization;
- results in a persistent or significant incapacity;
- results in a congenital anomaly/birth defect (not relevant to this study); or
- based upon appropriate medical judgment, may jeopardize the subject's health and may require medical or surgical intervention to prevent one of the other outcomes listed in this definition.

Definition of Adverse Device Effect (ADE)

Adverse Device Effect (ADE): Any untoward or unintended response to a medical device. This definition includes any event resulting from insufficiencies or inadequacies in the instructions for use or the deployment of the device or any event that is a result of user error.

This includes procedural events directly related to the TELLTALE BASILICA procedure and recovery from the procedure in addition to use of the investigational TELLTALE devices.

Definition of Serious Adverse Device Effect (SADE), Anticipated Adverse Device Effect (AADE) and Unanticipated Adverse Device Effect (UADE)

Serious Adverse Device Effect (SADE): An adverse effect that may have been or is attributed to the use of the device and produce an injury or illness that is life-threatening, results in permanent impairment or damage to the body, or requires medical or surgical intervention to prevent permanent harm to the body.

Anticipated Adverse Device Effects (AADEs): An AADE is an adverse event with a reasonable possibility that the device or procedure caused or contributed to the event. Please refer to the list of anticipated adverse device effects (AADE) in section 0 on page 21.

Unanticipated adverse device effect (UADE): Any serious adverse effect on health or safety or any life-threatening problem or death caused by, or associated with, a device, if that effect, problem, or death was not previously identified in nature, severity, or degree of incidence in the investigational plan or application (including a supplementary plan or application), or any other unanticipated serious problem associated with a device that relates to the rights, safety, or welfare of subjects.

Classification Adverse Events

Severity of Event

Category	Description
Mild	Awareness of symptom. Not expected to have a clinically significant effect on the subject's condition. Not surpassing the expected standard medical intervention.
Moderate	Condition creates a level of discomfort that interferes with the subject's usual activity or affects clinical status. May require medical intervention.
Severe	Incapacitating and significantly affects the subject's clinical status. Likely requires medical intervention and prolonged hospitalization.

Relationship (Attribution) to Study Intervention

Classification	Description
Definite	The event is clearly related to the research protocol.
Probable	The event is likely related to the research protocol. The event has a reasonable temporal relationship to the research device or research procedure and alternative causes, such as underlying disease, concomitant medications, or concomitant treatment-can be excluded.
Possible	The event may be related to the research protocol. The event has a reasonable temporal relationship to the research device or research procedure, and attribution of the event to the device or procedure cannot be excluded. However, alternative causes—such as underlying disease, concomitant medications, or concomitant treatments—are presumably responsible.
Unlikely	It is doubtful the event is related to the research protocol. The event can reasonably be explained by other factors, including underlying disease, concomitant medications, or concomitant treatments.
Unrelated	The event is clearly not related to the research protocol. There either is no temporal association with the research device or procedure, or the event is readily explained by other factors, including underlying disease, concomitant medications, or concomitant treatments.

Expectedness

Please see the list of anticipated adverse device effects (AADE) in section 0 on page 21.

The NHLBI Principal Investigator and the Participating Site Principal Investigator will be responsible for determining whether an adverse event (AE) is expected or unexpected. An AE will be considered unexpected if the nature, severity, or frequency of the event is not consistent with the risk information previously described for the study intervention.

Intervals and Frequency for Event Assessment and Follow-Up

Adverse event assessment, recording, and reporting will start on Day (0), upon attempt at a TELLTALE BASILICA-TAVR procedure and will continue through the 90 days follow up.

New events or conditions present at baseline that increase in severity will be recorded and evaluated and reported on the adverse event case report form.

All adverse events (AE) and adverse device effects (ADE) will be recorded and reported to the Sponsor using study specific case report forms, and then entry into the NIH electronic data base, CTDB (or equivalent), **through the 30 days follow-up**. All serious adverse device effects (SADE), serious adverse events (SAE), unanticipated device effects (UADE), and unanticipated problems (UP) will be recorded **through the 90 days follow up**. Adverse event case report forms and all source documentation supporting the adverse event will be transmitted to the Sponsor for review prior to entering the event into CTDB.

Adverse Event Reporting

Unanticipated adverse device effects (UADE) and Unanticipated problems (UP) must be submitted to the Sponsor for review and approval prior to submitting to the Reviewing IRB (Advarra). Sponsor will review, and if appropriate, provide suggestions to the site Principal Investigator. The enrolling site will then enter event into CTDB, and submit the report to Advarra in accordance with Advarra's policies. Sponsor will then submit final report to the NHLBI Office of the Clinical Director (OCD).

It is the responsibility of the site investigator to report adverse events and adverse device effects to their respective HRPP/IRB offices or other regulatory bodies according to their local institutional reporting requirements.

Reporting obligations and deadlines are summarized in Appendix B.

Site reporting to local institutional bodies

In addition to reporting to Advarra and the Sponsor, the Site Principal Investigator is responsible for further reporting of events to their own institution per local reporting requirements.

The NIH PI will report events to the NIH Office of Human Subjects Research Protections (OHSRP) in accordance with NIH HRPP Policy 801: Reporting Research Events found here:

<https://policymanual.nih.gov/3014-801>

Device Safety Reporting

The Sponsor is responsible for device safety reporting to FDA.

Investigators are required to submit a report of a UADE to the Sponsor. The Sponsor must immediately conduct an evaluation of a UADE and must report the results of the evaluation to FDA, Advarra, and participating investigators within 10 working days after the Sponsor first receives notice of the effect. Events of Special Interest

Not applicable

Reporting of Pregnancy

Not applicable

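### Section 9.4 sets a narrower seriousness test for device-caused events than for other events, so an anticipated device effect whose only serious feature is hospitalisation is handled as an ordinary ADE

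*Combined protocol and SAP*

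**What the plan says.** All of the definitions stand in Section 9.4 of the protocol.

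- **SAE.** The definition opens with "A serious adverse event that results in any of the following and NOT directly related to the device". Its list includes an event that "results in in-patient hospitalization or prolongation of existing hospitalization", and ends with a medical-judgment criterion.
- **SADE.** The effect must produce an "injury or illness that is life-threatening, results in permanent impairment or damage to the body, or requires medical or surgical intervention" and, for the last limb, the intervention must be "to prevent permanent harm to the body". Neither hospitalisation nor a general medical-judgment criterion appears.
- **Recording windows.** The subsection on intervals first says that adverse event recording starts at the attempted "procedure and will continue through the 90 days follow up". It then separates the classes. "All adverse events (AE) and adverse device effects (ADE) will be recorded and reported to the Sponsor using study specific case report forms", and entered in the database, "through the 30 days follow-up". For the serious and unanticipated classes, "All serious adverse device effects (SADE), serious adverse events (SAE), unanticipated device effects (UADE), and unanticipated problems (UP) will be recorded" through 90 days.

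The Schedule of Activities (Section 2.3) marks adverse event assessment at both the 30-day and the 90-day contact, each with a window of plus or minus 3 weeks. Section 2.4 lists bleeding with a prolonged hospital stay among the criteria for reporting a haemoglobin fall as either a serious AE or a serious ADE. Section 14.2 gives the site 3 working days to report a SADE, 5 for an SAE and 7 for an anticipated ADE.

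**The concern.** The trial exists to assess a device, yet an event is harder to call serious when the device caused it. The same admission is an SAE if judged unrelated and an ordinary ADE if judged directly device-related. The label controls how fast the sponsor hears of the event and, on the specific recording sentence, whether it is recorded at all after the 30-day visit.

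The 90-day contact was added after FDA feedback (Section 5.4), so the period after day 30 is one in which device-related safety information is wanted. The adjudication committee reviews only events within 30 days (Section 11.6). After that, adjudication does not correct a site's classification.

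**Working it through.** No sample size or power figure enters this point. The check sets the two definitions side by side, runs one test case through every class, and then works out the reporting and recording consequences.

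**1. The two lists (Section 9.4)**

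| Feature | SAE | SADE |
|---|---|---|
| Causality condition | Not directly device-related | Attributed, or possibly attributed, to the device |
| Death | Listed | Not named |
| Life-threatening | Listed | Listed |
| Admission or longer stay | Listed | Absent |
| Incapacity or impairment | Persistent or significant | Permanent |
| Birth defect | Listed, marked not relevant | Absent |
| Judgment or intervention | Judgment that intervention may be needed to avert a listed outcome | Intervention required to avert permanent harm |

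**2. Test case.** Take an event directly caused by the device that is on the anticipated list in Section 3.3. It leads to admission or a longer stay, is not life-threatening, leaves no permanent damage and needs no intervention to prevent permanent harm. Two examples are a TIA that resolves under observation, and haemolysis that causes a readmission for observation only. Section 3.3 lists both TIA and haemolysis.

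- SAE: no, because it is directly device-related.
- SADE: no, because no limb is met.
- UADE: no, because it was identified in advance. This assumes that its severity and frequency are also as anticipated.
- UP (Section 9.5): no, because it is expected, on the same assumption.
- ADE: yes.

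If the same event is judged not directly device-related, it is an SAE through the hospitalisation criterion.

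**3. Up to the 30-day visit.** The event is recorded, as an ADE. From Section 14.2, the site limit is longer by 7 − 3 = 4 working days than for a SADE and by 7 − 5 = 2 working days than for an SAE. Upstream, Section 14.1 sends an SAE to the Clinical Director within 14 calendar days, while an anticipated ADE goes into an annual summary. Section 14.1 has no line of its own for a SADE, so the upstream contrast is with the SAE line.

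**4. After the 30-day visit.** The specific ADE sentence ends recording. The opening sentence of the same subsection and the 90-day entry in Section 2.3 continue it, so the passages conflict. The nominal interval is 90 − 30 = 60 days. With both windows at 21 days:

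- latest 30-day visit: 30 + 21 = day 51; earliest 90-day visit: 90 − 21 = day 69; interval 69 − 51 = 18 days
- earliest 30-day visit: 30 − 21 = day 9; latest 90-day visit: 90 + 21 = day 111; interval 111 − 9 = 102 days

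**5. Consistency with Section 2.4.** That table treats a prolonged stay with bleeding as a criterion for a serious ADE. The SADE definition gives no basis for it, which suggests that the omission was not intended.

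**The case against.** The case against giving this much weight is substantial, and most of it stands.

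- The SAE exclusion reaches only events directly related to the device. An event that is indirectly or doubtfully related can still be an SAE.
- Many device-related admissions will involve treatment that meets the SADE intervention limb.
- An unexpected event can be a UP, which does not require seriousness and is recorded to 90 days.
- Stroke, Type 2 or greater bleeding, major vascular or structural complications, severe kidney injury and device-related intervention are in the 30-day composite. That composite is assessed again at 90 days as an exploratory endpoint (Section 4.7), so these events are collected whatever their label.
- Section 5.4 reports no new adverse events attributed to BASILICA after 30 days in the earlier IDE trial.

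Three stronger readings are tempting, and the documents do not support them.

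- **About 6 of 90 subjects affected.** A reader might take the 2 of 30 non-disabling strokes in the earlier IDE study (Section 3.2): 2/30 × 90 = 6. The protocol does not say whether those strokes were directly device-related, resolved, or needed no intervention, and stroke is captured by the composites. Other figures in Section 3.2 differ: the registry implies 2.8% − 0.5% = 2.3% non-disabling, about 2 of 90, and the interim look found no stroke or TIA in 27 treated subjects. None of these is a rate for the events at issue.
- **Device events after day 30 are not recorded at all.** This overlooks the opening sentence on intervals and the 90-day assessment in Section 2.3. The accurate statement is that the passages conflict.
- **The safety results are biased low.** Section 10.4 analyses no SADE count, and the stopping guidance in Section 10.5 uses 30-day mortality.

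What remains is the test case in the working. None of these objections changes its classification as an ADE.

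**Conclusion.** The point holds as a narrow defect in safety classification and reporting. An anticipated, directly device-related event whose only serious feature is hospitalisation falls outside SAE, SADE, UADE and UP. Up to the 30-day visit the cost is a wrong class and a site deadline 2 to 4 working days longer. After it, recording rests on contradictory text for a nominal 60 days, or 18 to 102 days across the visit windows. Prolongation of the index stay will mostly fall in the first period.

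The conclusion assumes that the definitions are applied as written and that the event is expected in nature, severity and frequency. The documents give no frequency for such events, so no count of affected subjects can be stated. The primary and secondary endpoints and the stopping guidance are unaffected. It should be corrected because the remedy is cheap and the asymmetry runs against the device question that the trial is meant to answer.

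**What to change.** - In Section 9.4, apply the seriousness criteria already printed for SAEs, including death and hospitalisation or prolongation, to all events. Then split by cause: serious and not device-related is an SAE; serious and possibly, probably or definitely device-related is a SADE. Take the device exclusion out of what makes an event serious.
- State that attribution to the device decides the split. The relationship scale in Section 9.4 is headed by relation to the research protocol, which also covers the procedure.
- Reconcile the opening sentence on intervals with the later 30-day and 90-day sentences, and with the schedule in Section 2.3, so that one recording window applies to each class.
- Align the Section 2.4 criteria with the SADE definition, and say in Section 14.1 which reporting line applies to a SADE.

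The cost is definition wording, a case report form check, and re-classification of ADEs already entered with a hospitalisation. The reported SADE count may rise slightly. The change affects safety reporting only, not the treatment of subjects or any endpoint definition.
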